(Max ¼ page) This research uses community based participatory research (CBPR) to engage low-income Latinx families in research to pilot test an adapted nutrition education program compared to an existing nutrition education program. The goal of the research is to provide nutrition education on healthy infant feeding to reduce risk for early childhood obesity.
--

11. What is the scholarly rationale for this study?

(Max ½ page)

The prevalence of obesity in early life remains unacceptably high, especially among low-income children, most are ethnic minorities. Marked ethnic disparities are evident by two years of age, which suggests that existing interventions are not adequate. Early prevention is critical, especially for low-income children. For example, among Latino children high body mass index during infancy renders them three times more likely than other children to be obese by age 6. The disparity observed at this young age presents a window of opportunity to intervene early through existing nutrition programs that foster healthful eating habits, which track into childhood and continue into adulthood. Yet, few prevention programs intervene during infancy, and those that do, do not incorporate feeding styles and practices into nutrition education, do not account for the involvement of caregivers other than parents in infant feeding, and/or 3) start too late. The proposed research addresses these gaps by moving beyond healthy eating to better understand and promote healthy feeding. This project, which focuses on an-at-risk child population, has great potential to address our nation's growing crisis of childhood obesity, which can dramatically improve the health of millions of low-income children, their families, and their future children.

12. What are the study hypotheses or research questions?

(Max ¼ page)

This research will implement and evaluate an existing healthy infant feeding intervention, Healthy Beginnings, which was developed for English-speaking low-income mothers in Australia and delivered by public health nurses via in-home visits. We will test the efficacy of an adapted version of this intervention in comparison to the original intervention.

Aim 1. Pilot test an adapted nutrition education program of, compared to the original program curriculum.

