- Using a pilot randomized control trial with 30 mother-infant-caregiver triad (15 intervention, 15 control) determine the feasibility, acceptability, and preliminary efficacy of the adapted intervention compared to the original intervention. We hypothesize that the adapted intervention will be feasible, acceptable to study participants, and efficacious in addressing feeding styles and practices and caregivers' role in infant feeding.

We anticipate that the intervention will be feasible to deliver and acceptable to mothers and caregivers, and that the mother—infant-caregiver triads randomized to intervention with the adapted Healthy Beginnings curriculum compared to the treatment as usual control group will demonstrate greater improvements in outcomes (i.e., infant feeding knowledge and use of recommended feeding practices) after 6 months compared to the control group.

III – Study Design and Methodology

13. Study Timelines

Estimated start date for involvement of participants: February 1, 2023 or upon approval of the IRB protocol.

Estimated completion date for the involvement of participants: Feb. 28, 2024

14. Location of Research

a) Where will this study take place? If there is an online component, provide details.

(Max ¼ page)

The research will be carried out in Inland Southern California, specifically communities of the Coachella Valley and surrounding area. The PI, [name] and Co-Investigator [name], along with graduate and undergraduate research assistants are located at UCR. Co-I, [name], and research coordinator/assistant, [name], is located at Brown University. Community Investigator, [name], is located in the Coachella Valley. All research takes place at UCR. The research will primarily engage Latinx and Indigenous Mexican (e.g., Purépecha) communities in Inland southern California.

b) Is this a collaborative or multi-site study? Yes No

- Collaborative or cooperative studies involve investigators from two or more institutions working together to conduct a research project. Different research activities can occur at different sites or the study can be a single-site study that involves personnel from multiple institutions.
- Multi-site studies use the same research procedures outlined in a single protocol that is carried out at multiple institutions (e.g., a clinical trial where participants will be enrolled at each participating site, or an educational intervention implemented at each participating site).

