The pilot RCT will include an intervention and control group and will be carried out over 6 months or 24 weeks and will involve 30 mother-infant-caregiver triads. Both mother and caregiver have to agree to participate in the study to be enrolled. If the caregiver declines, then the mother cannot participate; and vice versa if the mother declines, then the caregiver cannot participate. The eligibility screening tool asks mothers if another caregiver who cares for their infant at least 3 hours per week would be willing to participate in the study with them. If the mother answers no, then the mother is not eligible to participate in the study. Enrollment is ongoing and will begin the first week of every month from April to August 2023. The mother-infant-caregiver triad will be enrolled in the study upon recruitment and begin the study as soon as the infant is 4 months of age, which aligns with the dissemination of packet 1 that includes nutrition education for families of infants 4 to 6 months of age. In this design, participants will be randomized into the intervention or control group: intervention group will be Group A: Grow Well and will

receive the adapted Healthy Beginnings Curriculum (n= 15 mother-infant-caregiver triad) and the control group will be Group B: Healthy Steps and will receive the Healthy Steps curriculum or treatment as usual as this is the curriculum commonly shared during well baby visits (n= 15 mother-infant-caregiver triad). Randomization will occur once base-line data is collected. Comparisons will be made between the intervention and control groups during the first 6 months of the intervention. The focus is on Latinx Spanish-speaking families; however, all our material is in English and Spanish to accommodate language preferences. Additionally, if a mother or caregiver prefers Purépecha, a language commonly spoken in the region, a Purépecha-speaking team member can translate orally from Spanish to Purépecha as this is an oral and not written language.

Intervention Design

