WhatsApp group chat. Study team members will post weekly to a group chat that includes the mothers and caregivers in the intervention group (see *Appendix I. WhatsApp Posts*). The posts will include feeding information, infant nutrition, and caregiver communication. The posts are based on information provided in the adapted Healthy Beginnings 4–12-month booklets. The group chat will also be a virtual space for participants to interact and support each other. Mothers will be in one group chat and caregivers in a separate group chat. A team member will oversee this group and post weekly.

Group B - Healthy Steps. The control group will receive treatment as usual and will receive material frequently distributed throughout healthcare systems serving low-income patients. For the Healthy Steps curriculum for

infants 4 to 12 months of age packets are distributed at baby wellness visits at 4-, 6-, 9-, and 12-month visits (more information about the Healthy Steps program including handout material can be found here: <https://www.healthysteps.org/>). The Healthy Steps program provides information packets on developmental milestones, sleeping, and play (see *Appendix J. Healthy Steps Curriculum*). Healthcare providers hand out these packets to caregivers at the end of well-baby visits as take-home information. Mothers randomized to the control group will receive this information in the mail during first week of months 1, 3, and 5 of the study. The CHWs will call mothers the first week of months 1, 3, and 5 of the study to confirm receipt of the packets. Participants will be instructed to read the material. No other interaction will occur.

Zoom procedures

Zoom will be used for the orientation as well as baseline and follow up data collection and one-on-one interviews. We will create a password protected Zoom session with a unique link, meeting ID number and password per session that study team members will share directly with participants via text message or email (participants will be blind copied). Once participants enter the Zoom space, we will ask them to change their screen name to a pseudonym or will help them change the name, so their real name is not visible. Participants will have the option to keep their camera off or turn it on.

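### The comparator is described in three incompatible ways, and the protocol does not settle whether Group B receives feeding content, so the stated efficacy contrast is not the one the design delivers

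*Protocol*

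**What the plan says.** The protocol describes the comparator differently in different places.

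- **Section 10 (Abstract):** the study will "pilot test an adapted nutrition education program compared to an existing nutrition education program". The existing programme is not named.
- **Section 12, opening paragraph:** "We will test the efficacy of an adapted version of this intervention in comparison to the original intervention", where the intervention meant is Healthy Beginnings. Aim 1 and its bullet repeat the contrast with the original curriculum.
- **Section 12, closing hypothesis:** triads given the adapted curriculum "compared to the treatment as usual control group will demonstrate greater improvements in outcomes (i.e., infant feeding knowledge and use of recommended feeding practices".
- **Section 20a, design paragraph:** the control group "will receive the Healthy Steps curriculum or treatment as usual as this is the curriculum commonly shared during well baby visits".

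On control content, section 20a under Group B states: "The Healthy Steps program provides information packets on developmental milestones, sleeping, and play". The packets are mailed in months 1, 3 and 5, each with a call to the mother to confirm receipt, and then "No other interaction will occur".

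Two places bear on whether Group B also receives nutrition material. The section 20a design paragraph ties the start of the study at 4 months of age to "packet 1 that includes nutrition education for families of infants 4 to 6 months of age", without saying which arm gets that packet. Section 18 (Compensation) describes a welcome gift for mothers and caregivers that contains printed nutrition education material, with no restriction by arm. It then says that Group A's gift will also contain the Grow Well booklet.

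**The concern.** Group A is taught the subject that the efficacy outcomes measure: nutrition, mealtimes and responsive feeding. If Group B's material leaves feeding out, a Group A advantage in feeding knowledge or practices shows that the full Grow Well package does better than no study feeding education. That is a legitimate pilot question. It is not the question in the abstract (adapted against existing nutrition education) or in Aim 1 (adapted against original curriculum).

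What is at stake is the conclusion the trial may draw. A reader of the abstract or Aim 1 would take a positive difference as evidence that the adaptation adds something over a nutrition programme already in use. The design supports that reading only if the control is such a programme, and the protocol's own description of the control does not say that it is.

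**Working it through.** The protocol attaches no figure to this point, so the check is a comparison of the text plus a sum of scheduled contact.

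**Step 1. Who receives the stated comparator?**
- Original Healthy Beginnings (section 12, Aim 1): neither arm. Group A gets the adapted version and Group B gets Healthy Steps.
- An existing nutrition education programme (section 10): if this means Healthy Beginnings, again neither arm. If it means Healthy Steps, the label fits only if the Healthy Steps packets teach nutrition.
- Healthy Steps or treatment as usual (end of section 12, section 20a): Group B. This is the only description that matches an allocated arm.

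**Step 2. Do the Healthy Steps packets teach nutrition?**
- The Group B paragraph lists milestones, sleep and play. Feeding is not listed.
- The packet 1 sentence mentions nutrition education. Elsewhere the protocol uses the word packet only for Healthy Steps; Grow Well material is called booklets or modules. If packet 1 is Healthy Steps, this sentence and the Group B list disagree. If it is Grow Well material, they do not, and the sentence says nothing about Group B.
- The welcome-gift text in section 18 can be read as giving printed nutrition material to both arms, or as a loose description of what Group A receives.

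The text does not settle the question.

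**Step 3. Scheduled contact by arm (section 20a).**
- Group A mothers, home sessions: 6 × 30 = 180 to 6 × 45 = 270 min.
- Group A mothers, phone calls: 6 × 15 = 90 to 6 × 20 = 120 min.
- Group A mothers, total: 180 + 90 = 270 to 270 + 120 = 390 min (4.5 to 6.5 h).
- Group A caregivers, home sessions only: 180 to 270 min.
- Both also receive weekly posts over 24 weeks, about 24 in all.
- Group B: three mailings and three receipt calls to mothers, call length not given.

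The minutes are total contact. Sessions also cover communication, conflict resolution, self-care and goal setting, and the calls review those goals. No split is given, so time on feeding is an unknown part of the total.

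**Step 4. What a difference would mean.** If the Group B list is complete, the arms differ in topic, mode and amount of contact together. The contrast is the whole package against printed material without study feeding education. The protocol gives no effect size, so how far this contrast exceeds one against a true nutrition comparator cannot be computed.

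**The case against.** The strongest reply is that the closing hypothesis and the procedures already name a treatment-as-usual control, and that differing from usual care in content is what such a design tests. That is fair. It means the arms need not change. It does not repair the abstract, the opening of section 12 or Aim 1, which promise another contrast.

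A second reply is that the abstract's existing programme probably means Healthy Beginnings, which section 12 itself calls existing and which is a feeding programme. This is plausible, but no arm receives the original curriculum, so the stated contrast is still not delivered.

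A reader might go further and infer that Group B is an untaught arm on feeding. The protocol does not support that as a fact. The Healthy Steps list is a single summary sentence that does not claim to be complete and points to Appendix J, which is not available here. The packet 1 and welcome-gift passages can be read the other way. The feeding advice that families receive at ordinary well-baby visits is not described. Nor can the 270 to 390 minutes be read as feeding instruction.

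**Conclusion.** The point holds as an inconsistency with a conditional consequence. The comparator is described in three ways that cannot all be true, and only Healthy Steps or treatment as usual corresponds to an arm. That part needs no assumption. The trial as written cannot estimate the effect of adapting Healthy Beginnings against the original, because nobody is given the original.

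The further consequence, that a difference could not show superiority over an existing nutrition programme either, rests on one assumption: that the Group B content list is complete and no other study material gives Group B feeding content. The protocol leaves this open. Under that assumption the contrast is 270 to 390 minutes of contact for mothers and 180 to 270 for caregivers, plus about 24 posts, against three mailings on other topics and three receipt calls. The size of any resulting overstatement cannot be derived from the document. For a pilot of 30 triads this should be corrected, but it does not invalidate the design.

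**What to change.** 1. Reconcile section 10, section 12 with Aim 1, the welcome-gift text in section 18, and the packet 1 and Group B text in section 20a. State plainly whether any material given to Group B covers feeding, and which arm receives packet 1 and the nutrition material in the welcome gift.
2. Reword the abstract, the opening of section 12 and Aim 1 so that the efficacy claim is Grow Well versus Healthy Steps or treatment as usual.
3. If Group B has no feeding content, add to section 12 that a difference in feeding knowledge or practices estimates the whole Grow Well package against no study feeding education. State that it will not be reported as superiority over an existing nutrition programme or as the effect of the adaptation.
4. If the packets do contain feeding content, correct the Group B description to say so.

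The cost is protocol wording only, with a slightly less favourable claim. Arms, sample size and procedures stay as they are.

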participant's preference; each survey will last about 30-45 minutes. The survey will collect data on sociodemographic questions (e.g., income, education, language, mental health), infant feeding practices using the validated Infant Feeding Scale Questionnaire (Thompson et al., 2009), communication skills and conflict resolution strategies around feeding between the mother and other caregiver, and questions about breastfeeding, formula feeding, and family mealtimes (see *Appendix L. Pretest and Posttest Survey for Caregivers* and *Appendix M. Pretest and Posttest Survey for Mothers*). All participants (mothers and caregivers) will receive \$75 for completion of the pretest data collection and \$125 for completion of the posttest data collection. The purpose of an increased amount from baseline to follow-up is to compensate participants for the completion of the brief satisfaction surveys throughout the study and retain participants in the study over six months. (While only Group A participants will complete the brief satisfaction surveys, for purposes of equity all participants will receive \$125 at the end of the study.) In the final week of the study (week 24), study team members will administer the posttest surveys. The posttest survey will include the same questions as the pretest survey except it will not include the socio-demographic questions and will include a satisfaction survey. Only participants assigned to Group A – Grow Well will respond to the satisfaction survey questions. Participants can refuse to answer or skip any questions in either the pretest or posttest survey. If participants exit out of the study, their data will be removed from analysis.

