Anthropometric data collection. Anthropometric data will be collected at baseline and follow up. Because data will be collected at the CVFC, held the 2nd Saturday of the month, baseline data will be collected in week 2 of the intervention and follow up data in week 22. Trained medical students and CHW study team members will collect anthropometric data, weight, length, and body fat composition from infants at the beginning and end of the study period. We will collect infant weight using an infant scale, length using an infant measuring device that infants lay on, and body fat composition using fat calipers (see *Appendix N. Anthropometric Data Collection*). Mothers will be invited to bring their baby to the clinic for the purposes of data collection. However, if a mother is unable to bring their baby to the clinic, a study team member will collect data at the mother's home. Data collection will take approximately 10-15 minutes. [name] who is trained in infant anthropometric data collection will train study team members to collect and record these data prior to data collection. Participation in the study require infant anthropometric data collection. If participants exit out of the study, their infant's anthropometric data will be removed from analysis.

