During the consent process participants will be made aware that de-identified data sources including the transcripts of interviews, survey data, and infant anthropometric data will be de-identified. All records that include participants identifiers, such as the tracking files and audio files will be deleted after data collection and analysis. Participants will be informed that they can opt out of the study at any point during the 24-week study period and request for their data to not be included in the research. All participants will receive a study identification number to maintain confidentiality and privacy for all data collected. All data will be kept in a password-protected folder on the SOM secure server; once the data have been analyzed any records will be deleted (see Appendix T. Randomized Controlled Trial Consent – Mothers and Appendix U. Randomized Controlled Trial – Caregivers).

For mothers and caregivers in the intervention group (Group A- Grow Well), they will be given the option to opt into the satisfaction one-on-one interview and will be asked to provide their verbal consent (see Appendix Z. Consent – Participant Satisfaction Interview).

For the CHWs and healthcare staff in the one-on-one feasibility interviews they will be asked to provide their verbal consent (see Appendix V. Feasibility Consent - Community Health Workers and Healthcare Staff).

b) If you are applying for a waiver of documented consent (e.g., verbal, online, etc.) or a waiver or alteration of the consent process (e.g., not obtaining consent at all), please explain how you are meeting the conditions for the waiver or alteration as outlined in the [UCR informed Consent Guide](#).

(Max ¼ page)

In addition to written informed consent, we are also requesting a waiver of documented consent for data that will be collected via Zoom or phone. The electronic consent form will be on the Qualtrics platform and will be administered orally to all participants who will also be provided an electronic version of the consent form via the chat in Zoom or if calling into the Zoom platform, we will text or email them the consent form.

24. Will anyone other than the participants provide consent (e.g., parents, guardians, legally authorized representatives, etc.)? Describe the process by which capacity/competency will be assessed.

(Max ¼ page)

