Because we will include infants who are approximately 4 months old, the mother enrolled in the study will provide consent for their infants to participate in the study. Specifically, infants will be involved in the collection of anthropometric measurements. If mothers chose not to provide consent for their infants to participate in anthropometric measurements, they will still be able to participate in the study

25. Withdrawal: Where applicable, please describe how participants will be informed of their right to withdraw from the study and outline the procedures that will be followed to allow them to exercise this right. Also, what will happen if data has already collected (e.g. previous data will be kept, all data will be destroyed, etc.)?

(Max ¼ page)

The consent form contains language indicating participants' right to withdraw from the study at any point. During the consent process, participants will be informed that they can opt out of the study at any point during the 24-week intervention study period or during the qualitative interviews (if they opt into this data collection activity) and request for their data to not be included in the research. At the beginning of the study, participants will receive a study identification number that will be linked to the data they provide. We will create a document that includes the participant's name and study ID #. Only select members of the investigative team, including [name] (PI), the project coordinator ([name]), and graduate student researcher ([name]) will have access to this file, which we will store on a password protected file on the UCR SOM server. Once all data collection is complete, we will destroy this file.

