Thus, during the consent process, participants will be informed of their right to withdraw from the study at any time both in writing via the consent document and verbally from the consenting study investigator/team member. When reviewing the consent forms, the interviewer will inform participants about the voluntary nature of their participation and their right to withdraw from the study at any point during the research. The study team member will make clear the following: 1) the participant can notify the study investigators/staff of their wish to withdraw and 2) after confirmation of withdrawal; all data collected from the participant will be destroyed and will not be included in study analyses or deliverables. Participants will be able to leave any data collection activity at any time and can withdraw from the study at any point. Withdrawal will not affect their relationship to UCR or partnering healthcare systems such as UCR Health or the CVFC.

All data will be kept in a password-protected folder on the SOM secure server; once the data have been analyzed any records will be deleted.

26. Privacy, Confidentiality & Data

- a) **Privacy: Where and how will participants be providing information? Are the researchers collecting identifying information (e.g., names, addresses, phone numbers, DOBs, phone numbers, licenses, audio/video recordings, etc.)? If yes, please describe:**

(Max ¼ page)

Researchers will obtain participants' contact information, including cell phone and email address, to share information on accessing the Zoom platform and to call participants to schedule and conduct interviews. Postal addresses will also be obtained to mail out participant incentives (e.g., gift cards, welcome gift). Phone numbers, email addresses, and postal addresses will only be used for the purposes of data collection and compensation. The consent forms include an option to opt into future research on the health and wellbeing of Latino and Indigenous Latin American communities. For all those who opt into future research, their names and contact information will be recorded in a separate database only accessible to study team members.

To protect participant information when we collect survey data, we will remove all responses regarding incentive payment (e.g., address to send gift card) and place it on a separate document then delete the information once payment has been sent.

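### The protocol gives conflicting rules for leavers' data: automatic removal on exit, exclusion on request, and destruction after confirmed withdrawal

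*Protocol*

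**What the plan says.** Three rules for a leaver's data appear in the protocol.

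- **Removal on exit (item 20a).** Under 'Baseline and follow up data collection': "If participants exit out of the study, their data will be removed from analysis". Under 'Anthropometric data collection', on exit the infant's "anthropometric data will be removed from analysis". No request is needed, destruction is not mentioned, and exit is not defined.
- **Exclusion on request (items 23a and 25).** The consent section says participants will be told that they can "opt out of the study at any point during the 24-week study period and request for their data to not be included". The first part of the withdrawal section repeats this: they may opt out and "request for their data to not be included in the research". Neither place says what happens if no request is made.
- **Destruction after confirmed withdrawal (item 25, later paragraph).** Participants will be told that "the participant can notify the study investigators/staff of their wish to withdraw" and that "after confirmation of withdrawal; all data collected from the participant will be destroyed and will not be included in study analyses or deliverables". No separate request about data is required. The same paragraph adds: "Participants will be able to leave any data collection activity at any time and can withdraw from the study at any point".

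Item 20a also says that randomisation takes place after baseline data are collected.

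**The concern.** The rules have three triggers (exit, request, confirmed withdrawal), and their consequences differ. Staff handling a leaver's records could follow any of them and be within the protocol. Three things are at stake.

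1. **The comparison.** An exit once baseline is complete falls after randomisation. Removing that person's data selects the analysed groups on a post-randomisation event. Contact differs sharply by arm: Group A has monthly home sessions, monthly calls and weekly group posts; Group B has mailed packets and three calls to confirm receipt. Reasons for leaving, and the leaving rate, may therefore differ by arm.
2. **What can be checked later.** An analysis plan can set aside the removal rule if the data still exist. It cannot bring back destroyed data, so whether withdrawers differed at baseline could no longer be examined.
3. **Acceptability, a stated aim.** Group A gives brief satisfaction ratings after each session and call. The other participant-reported sources come at week 24 (posttest satisfaction questions) or after the six months (interviews). The brief ratings may be the only satisfaction data an early leaver gave. If they carry the study ID, destruction would remove them too.

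**Working it through.** No figure in the protocol needs reproducing, so the check is mainly a comparison of the rules by type of leaver.

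| Leaver | Item 20a | Item 23a and first part of item 25 | Later part of item 25 |
|---|---|---|---|
| Leaves silently | Out of analysis, if this counts as exit | No request, so retention is implied | Not triggered |
| Gives notice, withdrawal confirmed, no data request | Out of analysis; destruction not mentioned | Retention is implied | Destroyed and out of analysis |
| Gives notice, withdrawal confirmed, asks for data to be left out | Out of analysis | Out of the research | Destroyed and out of analysis |
| Stops home sessions or calls but would still give data | Unclear, as exit is undefined | Unclear | Separates leaving a data collection activity from withdrawing, but does not mention sessions |

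For the analysis set, the rules conflict in the first two rows: excluded, or included by implication. For the fate of the data, the second row has two written results (removed, destroyed) and one implied (kept). Only the later part of item 25 orders destruction of a leaver's data.

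**What one exit means in numbers.** Inputs from the protocol: 15 triads per arm, two surveyed adults and one infant per triad.

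- Adult pretests per arm: 15 × 2 = 30.
- One triad: 2/30 = 6.7% of its arm's adult pretests, and at most 1 of 15 infant sets. This is a maximum because item 24 lets a mother stay in the study "If mothers chose not to provide consent for their infants to participate in anthropometric measurements".
- With *e* triads exiting an arm and both adults leaving, item 20a leaves 30 − 2*e* pretests in that arm. The protocol gives no value for *e*. Assuming *e* = 2, 3 or 5 gives 26, 24 or 20 of 30.
- If *a* of those *e* triads are notified and confirmed withdrawals, item 25 destroys 2*a* pretests and at most *a* infant sets. For an assumed *e* = 3, *a* = 0, 1, 2 or 3 gives 0, 2, 4 or 6 pretests destroyed.

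**Brief ratings.** A Group A triad can give at most 6 sessions × 2 adults + 6 calls × 1 mother = 18. A triad leaving after month 3 could have given up to 3 × 2 + 3 × 1 = 9. Both figures assume every brief survey is completed. Whether these ratings can be tied to a person is not settled: item 23a gives participants an ID for all data collected, but the linkage list in item 26b does not name the ratings.

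These are counts of records, not estimates of bias. A bias estimate would need leaving rates by arm and the difference between leavers and stayers, and the protocol gives neither.

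**The case against.** The strongest reply is that the written rules largely agree on who is analysed. Item 20a and the later part of item 25 both exclude the leaver, and that part opens as a summary of what precedes it. On this view the request clause is loose drafting. Someone who withdraws before week 24 has no posttest, so keeping the pretest adds little to a six-month comparison. Destroying data on withdrawal is also a defensible protection for a population that the protocol itself calls vulnerable. Definitions of exit and of analysis sets are often left to a statistical analysis plan, and the consent forms, which fix what was promised, are not shown.

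Much of this stands. It narrows the point in four ways, each countering a stronger reading that a reader might infer.

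- *That the protocol states three outcomes for every leaver.* It does not. Retention under items 23a and 25 is only implied, although a right to request exclusion would add little if exclusion were automatic. A silent leaver never triggers the destruction rule.
- *That destruction on withdrawal is the only irreversible step.* This holds only among the leaver rules. Item 25 also has the file linking names to IDs destroyed once data collection ends, and items 23a and 25 have records deleted after analysis. Those steps apply to everyone. Nor does item 20a say whether removed data are kept.
- *That acceptability will be overstated.* That would need leavers to be less satisfied than stayers and the ratings to be ID-linked. The protocol establishes neither.
- *That the gap lies in a missing definition.* An undefined exit alone could be left to an analysis plan. The finding is that the protocol states a rule, and states it inconsistently.

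The reply does not remove the conflict between automatic and on-request exclusion. Nor can an analysis plan recover destroyed data or alter what participants were told.

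**Conclusion.** The conflict is real and should be fixed. Item 20a removes data automatically on an undefined exit. Items 23a and 25 make exclusion depend on a request. Item 25 also orders destruction after a notified and confirmed withdrawal. For a silent leaver only the first two conflict; for a confirmed withdrawer who makes no data request all three do. Followed as written, removal and destruction drop randomised participants on a post-randomisation event, and destruction rules out a later baseline comparison of those who withdrew.

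The size and direction of any bias cannot be determined from the protocol. The conclusion rests on the wording and on randomisation following baseline, not on any assumed dropout rate. The loss of satisfaction ratings depends on their being ID-linked, which is unconfirmed. What participants were actually promised cannot be checked without the consent forms.

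**What to change.** Reconcile item 20a (surveys and infant measurements), item 23a, item 25 and the consent text into one rule, using the on-request wording already in items 23a and 25:

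- Keep data collected before exit, including brief satisfaction ratings, and analyse them in the randomised group unless the participant asks for deletion.
- Define exit so that stopping the sessions or calls is separate from withdrawing from data collection.
- Still offer the planned posttest and infant follow-up to families who only stop sessions.
- Report exits and deletion requests by arm, out of all randomised triads.
- Honour the promise already made to anyone consented under the destruction wording.

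**Cost.** Wording changes, an IRB-approved consent amendment and some incomplete records to handle in analysis. No participants are added; any extra posttests and infant measurements fall within the planned 30 triads. If enrolment has begun, two data rules may run in one small trial. If it has closed, only the removal rule in item 20a and the by-arm reporting can still be changed.
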